4.1.4.5 Recommendations for dose modification in response to AEs

AEs should be assessed for relatedness as outlined in [Section 5.3.6](#). In case an AE is considered related to ibrutinib, recommendations for dose modifications for ibrutinib should be considered. In case an AE is considered related to BI 836826, recommendations for dose modifications for BI 836826 should be followed. In case an AE is considered related to both ibrutinib and BI 836826, it is at the discretion of the investigator whether to modify the dose for both drugs at the same time, or only for one drug.

Dose modifications for adverse events related to ibrutinib:

Ibrutinib will be used within the approved label indication as per clinical routine. The following recommendations as per label should be considered by the investigator when administering ibrutinib:

‘Interrupt ibrutinib for

- any Grade 3 or greater non-hematological,
- Grade 3 or greater neutropenia with infection or fever, or
- Grade 4 hematological toxicities.

Once the symptoms of the toxicity have resolved to Grade 1 or baseline (recovery), ibrutinib may be reinitiated at the starting dose. If the toxicity reoccurs, reduce dose by one capsule (140 mg per day). A second reduction of dose by 140 mg may be considered as needed. If these toxicities persist or recur following two dose reductions, discontinue ibrutinib.’

Dose modifications for adverse events related to BI 836826

Worst NCI CTCAE Grade after previous dose	BI 836826
Neutrophil values at nadir after previous dose	
< LLN and $\geq 1 \times 10^9/L$	Maintain current dose level and schedule
< $1 \times 10^9/L$ and $\geq 0.5 \times 10^9/L$ or < $0.5 \times 10^9/L$ for ≤ 7 days	Monitor neutrophils until recovery. Delay BI 836826 until Grade ≤ 2 . Thereafter resume at full dose.
< $0.5 \times 10^9/L$ for >7 days	Monitor neutrophils until recovery. Delay BI 836826 until Grade ≤ 2 . Thereafter may resume at full dose. Consider G-CSF support. If neutropenia Grade 4 for > 7 days recurs despite G-CSF support in subsequent cycle, the dose of BI 836826 should be reduced to 50%.
Thrombocytopenia	
PLT > 10 000/ μ L	Maintain current dose level and schedule
PLT $\leq 10 000/\mu$ L at two separate measurements (at least 24 hours apart)	Monitor thrombocytes until recovery to Grade 3. Consider platelet transfusion. Delay BI 836826 until Grade ≤ 3 (recovery). Upon recovery, BI 836826 may be resumed at full dose. If a level of PLT $\leq 10 000/\mu$ L, at two separate measurements at least 24 hours apart, recurs in the subsequent cycle, dose of BI 836826 should be reduced by 50%.
Hepatic Adverse Events (elevations in ALT, AST)	
Grade ≤ 1 (ALT/AST $\leq 3 \times$ ULN)	Maintain current dose level and schedule
Grade 2 (ALT/AST >3 and $\leq 5 \times$ ULN)	Delay BI 836826 until Grade ≤ 1 . Thereafter resume at full dose.
Grade 3 or 4 (ALT/AST >5 and $\leq 20 \times$ ULN)	Withhold BI 836826. Monitor ALT/AST at least 1x per week until Grade ≤ 1 . Thereafter, may resume at full dose. If ALT/AST elevation Grade ≥ 3 recurs with BI 836826 at full dose, reduce BI 836826 by 50%. Reescalation of BI 836826 upon resolution of symptoms to 100% possible at

Worst NCI CTCAE Grade after previous dose	BI 836826
	the investigator's discretion in later infusions.
Hepatic Adverse Events (elevations in bilirubin)	
Grade ≤1 (bilirubin ≤1.5 x ULN)	Maintain current dose level and schedule
Grade 2 (bilirubin >1.5 and ≤3.0 x ULN)	Delay BI 836826 until Grade ≤1. Thereafter resume at full dose.
Grade 3 or 4 (bilirubin >1.5 and ≤3.0 x ULN)	Withhold BI 836826. Monitor bilirubin at least 1x per week until Grade ≤1. Thereafter, may resume at full dose. If bilirubin elevation Grade ≥3 recurs with BI 836826 at full dose, reduce BI 836826 by 50%. Reescalation of BI 836826 upon resolution of symptoms to 100% possible at the investigator's discretion in later infusions.
Other Non-haematological Adverse Events	
Grade ≤2	Maintain current dose level and schedule
Grade ≥3	Withhold study drug until Grade ≤1. Study drug may be resumed at initial or lower dose level or discontinued at investigator's discretion.

A dose reduction of BI 836826 may be performed twice as outlined in the next table. In case an AE recurs or persists following two dose reductions, BI 836826 should be discontinued.

Occurrence of a BI 836826 related AE included in previous table	BI 836826 Dose Modification at subsequent Infusion
First	Restart at assigned dose
Second	Reduce BI 836826 by 50% at next infusion (dose level -1)
Third	Reduce dose level -1 by 50%, i.e. reduce initially assigned dose of BI 836826 by 75% at next infusion (dose level-2)
Fourth	Discontinue BI 836826

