The term AESI relates to any specific AE that has been identified at the project level as being of particular concern for prospective safety monitoring and safety assessment within this trial, e.g. the potential for AEs based on knowledge from other compounds in the same class. AESI need to be reported to the Sponsor's Pharmacovigilance Department within the same timeframe that applies to SAE, see [Section 5.3.7](#).

The following events are considered as AESIs:

1. Hepatic injury
2. Late onset infections
3. Any AE qualifying for a DLT

Hepatic injury:

Although rare, drug-induced liver injury is under constant surveillance by sponsors and regulators and is considered an AESI. Timely detection, evaluation, and follow-up of laboratory alterations of selected liver laboratory parameters to distinguish an effect of the underlying malignancy on liver function from other causes are important for patient safety.

In patients with normal transaminases and bilirubin at baseline, a hepatic injury is defined by any of the following alterations of hepatic laboratory parameters:

- an elevation of AST and/or ALT ≥ 3 fold Upper Limit of Normal (ULN) combined with an elevation of total bilirubin ≥ 2 fold ULN measured in the same blood sample, and/or
- marked peak aminotransferase (ALT, and/or AST) elevations ≥ 10 fold ULN.

In patients with elevated transaminases and/or bilirubin at baseline in line with in- and exclusion criteria of this protocol, a hepatic injury is defined by the following alterations of hepatic laboratory parameters:

- an elevation of AST and/or ALT >5 fold ULN combined with an elevation of total bilirubin >2 fold ULN measured in the same blood sample, and/or
- marked peak aminotransferase (ALT, and/or AST) elevations ≥ 10 fold ULN.

These lab findings constitute a hepatic injury alert and the patients showing these lab abnormalities need to be followed up according to the "Drug Induced Liver Injury (DILI) checklist" provided via the RDC-system and within the ISF.

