Work-up as outlined in the "DILI-checklist" will serve to confirm the initial abnormality, obtain a comprehensive history and medical assessment, assess the severity of liver injury, evaluate data for potential alternative causes and decide on management of trial drug. Follow up of the potential DILI case should be initiated within 48 hours of the initial laboratory alert, or as soon as possible if timelines cannot be met. When performing all of the required examinations, the investigator may use clinical judgement, based on the patient's disease, comorbidities, clinical situation, past viral infections and risk for reactivation, exposure, prior therapy for malignant disease, co-medications and other factors as applicable. The sequence of tests in the DILI checklist may be used as guidance. The findings from the hepatic imaging (including comparison to prior imaging if available) must be made available as soon as

possible as part of the AE reporting process and/or on the respective CRF pages. In the event the etiology of the abnormal liver test results is not identified based on the imaging (e.g. biliary tract, pancreatic or intrahepatic pathology), the “DILI checklist” must be completed. Virus reactivation should be assessed by viral load and PCR testing where possible. Diagnostics for auto-immune hepatitis, Wilson’s disease and hemochromatosis can be completed at the end of all assessments, as these examinations will not change within a short time period but can be considered proof of a long persisting chronic condition. In case a laboratory parameter of the DILI checklist cannot be performed, the investigator should provide a comment including a brief assessment of the relevance of this parameter for the overall evaluation of DILI.

In case of clinical symptoms of hepatic injury (icterus, unexplained encephalopathy, unexplained coagulopathy, right upper quadrant abdominal pain, etc.) without lab results (ALT, AST, total bilirubin) available, the investigator should make sure these parameters are analysed, if necessary in an unscheduled blood test. Should the results meet the criteria of hepatic injury alert, the procedures described in the DILI checklist should be followed.

If the investigator determines any AESI is related to study drug, the administration of the study drug must be managed according to [Section 4.1.4](#) of the protocol.

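### The BI 836826 dose-modification table gives bilirubin Grade 2 and Grade 3 or 4 the same numeric range, leaving no range for values above 3.0 x ULN

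*Protocol*

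**What the plan says.** Protocol Section 4.1.4.5 tabulates what to do with BI 836826 after an adverse event, by worst CTCAE grade since the previous dose. The bilirubin block has three rows:

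- Grade 1 or lower is given as bilirubin up to 1.5 x ULN, with dose and schedule unchanged.
- The next row is "Grade 2 (bilirubin >1.5 and ≤3.0 x ULN". BI 836826 is delayed until Grade 1 or lower and then resumed at full dose.
- The last row is "Grade 3 or 4 (bilirubin >1.5 and ≤3.0 x ULN". BI 836826 is withheld, with the instruction "Monitor bilirubin at least 1x per week until Grade" 1 or lower is reached. Full dose may then be resumed. If Grade 3 or higher recurs at full dose, the dose is halved, and the investigator may later re-escalate.

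A second table in the same section sets dose steps by number of occurrences. At the second occurrence of a related event it says "Reduce BI 836826 by 50% at next infusion (dose level -1").

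On the status of the table, the section says "In case an AE is considered related to BI 836826, recommendations for dose modifications for BI 836826 should be followed". Section 5.3.6.1 adds, for adverse events of special interest (AESIs), "If the investigator determines any AESI is related to study drug, the administration of the study drug must be managed according to" Section 4.1.4.

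**The concern.** Two rows with different instructions carry one numeric range, and the range that should belong to the more severe row is not printed. The grade label and the number in that row cannot both be right.

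The choice of row matters most for monitoring. From Cycle 5, infusions are every four weeks and Day 15 visits are not required (Flow Chart, footnote 1), so scheduled safety laboratory tests are about four weeks apart. Only the Grade 3 or 4 row requires weekly bilirubin in between. The table also feeds the check before each full dose: Section 4.1.4.4 requires recovery from adverse events and refers to Section 4.1.4.5 for it.

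Hepatic injury is an AESI. Its combined criterion in Section 5.3.6.1 is a transaminase rise "combined with an elevation of total bilirubin" of at least 2-fold ULN with normal baseline values, or above 2-fold with elevated baseline values. Every bilirubin value that meets it lies where the printed ranges give two rows or none.

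**Working it through.** No statistical formula applies. The check is whether the printed ranges are mutually exclusive and cover all values.

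**Inputs**, all from Section 4.1.4.5, with x = bilirubin as a multiple of ULN:

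- Grade 1 or lower: x ≤ 1.5
- Grade 2: 1.5 < x ≤ 3.0
- Grade 3 or 4 as printed: 1.5 < x ≤ 3.0
- Grade 3 or 4 if the order of the rows is continued: x > 3.0

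**Number of rows matched by value alone:**

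| x (multiple of ULN) | As printed | With x > 3.0 in the last row |
|---|---|---|
| 1.0 | 1 | 1 |
| 1.5 | 1 | 1 |
| 2.0 | 2 | 1 |
| 3.0 | 2 | 1 |
| 3.1 | 0 | 1 |
| 10.0 | 0 | 1 |

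As printed, only values up to 1.5 x ULN point to exactly one row. From the AESI bilirubin threshold of 2 x ULN upwards, none does. With the corrected range, every value points to exactly one row.

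**Is this a copying slip or intended?** The ALT/AST rows directly above step up as expected: Grade 2 is above 3 and up to 5 x ULN, and the next row begins "Grade 3 or 4 (ALT/AST >5 and" ends at 20 x ULN. Only the bilirubin block repeats a range. The digits are intact and the text is current, not part of the amendment log.

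**What differs between the two rows:**

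| | Grade 2 row | Grade 3 or 4 row |
|---|---|---|
| Hold until | Grade 1 or lower | Grade 1 or lower |
| Weekly bilirubin | not stated | required |
| Full dose afterwards | directed | permitted |
| Recurrence rule in the row | none | halve the dose; re-escalation optional |

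The last difference is small, because the occurrence table already halves the dose at a second related event.

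**Reach into the primary analysis.** Section 5.3.6.2 defines dose-limiting toxicity by grade and does not use this range. The DLT count, the Bayesian logistic regression model and the MTD do not depend on it.

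**The case against.** The strongest reply is that the table is organised by CTCAE grade and the range in brackets is only a gloss. Section 5.3 grades laboratory changes by CTCAE version 4.0, the Grade 2 row stops at 3.0 x ULN, and the recurrence rule in the faulty row is itself written by grade. A site that grades first will probably act as intended. This stands, and it limits the consequence. It does not make the printed number right.

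No reading leads to dosing through raised bilirubin. Both rows hold the drug. A reader who found no range above 3.0 x ULN might turn to the row for other non-haematological events, which also withholds at Grade 3 or higher. This stands as well. What remains in doubt is monitoring and resumption, not the hold.

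The AESI argument is weaker than it first looks. The combined criterion also needs raised transaminases, so these patients nearly always fall under the ALT/AST rows too. Those rows require weekly ALT/AST monitoring above 5 x ULN. The patients also enter the liver-injury work-up of Section 5.3.6.1, with follow-up to start within 48 hours. The monitoring gap is therefore smaller for them than for a patient with an isolated bilirubin rise.

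Exposure is limited. Recruitment has stopped (Section 2.1), and Section 1.2.1 reports the drug-related transaminase rises in the monotherapy trial as free of concomitant bilirubin elevation. That does not exclude isolated rises, and patients on treatment may continue, for qualifying responders up to 24 cycles.

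**Conclusion.** The point holds: the Grade 3 or 4 bilirubin range is wrong as written. One of three bilirubin ranges is affected. By number alone, values above 1.5 and up to 3.0 x ULN match two rows and values above 3.0 x ULN match none.

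The effect is confined to weekly bilirubin monitoring, directed versus optional resumption at full dose, and a small difference on recurrence. It concerns patients still on treatment. No endpoint or model output changes. How often the row would be used cannot be judged from the documents, and the ambiguity arises only where a site reads the number instead of the grade.

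The correction is still worth making, because a hepatic-safety rule should not depend on readers disregarding its printed threshold. The corrected bound of 3.0 x ULN assumes that the Grade 2 range is the right one, as the order of the rows indicates.

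**What to change.** In Section 4.1.4.5, change the last bilirubin row to: Grade 3 or 4 (bilirubin >3.0 x ULN). The bound comes from the table's own Grade 2 upper limit and should be confirmed clinically.

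As an optional tidy-up in the same change, drop the upper limit of 20 x ULN from the ALT/AST Grade 3 or 4 row, so that it reads ALT/AST >5 x ULN. There is no conflict there, since only that row can plausibly apply above the limit.

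The cost is the wording of one table entry, or two with the tidy-up, by clarification letter or amendment. No patients, visits or data are added.

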3.3.4 Removal of patients from therapy or assessments

3.3.4.1 Removal of individual patients

An individual patient may be withdrawn from BI 836826 trial treatment if:

- Disease progression as assessed by investigator
- Initiation of any other new anticancer therapy for CLL, in the absence of disease progression
- The patient withdraws consent for study treatment or study participation, without the need to justify the decision.
- The patient is not able to tolerate a second re-challenge for the same AE (see [Section 4.1.4.5](#))
- The patient needs to take concomitant drugs that interfere with BI 836826, ibrutinib, or the trial results evaluation (see [Section 4.2.1](#) and [4.2.2](#))
- The patient can no longer be treated with trial medication for other medical reasons (such as another severe intercurrent illness, pregnancy, or breastfeeding)

In the last two cases, consultation with the BI Clinical Monitor is recommended.

Given the patient's agreement, the patient will undergo the procedures for early treatment discontinuation and follow up as outlined in the [Flow Chart](#) and [Section 6.2.3](#).

For all patients the reason for withdrawal (e.g. adverse events) must be recorded in the eCRF. These data will be included in the trial database and reported.

All withdrawals will be documented and the reason for withdrawal recorded and discussed, as necessary in the final report of the trial. As soon as a patient is withdrawn from the trial, the next scheduled visit and the EOT have to be performed if feasible. Every effort should be made to follow-up patients in case an AE is still ongoing at the time of withdrawal.

If a patient should become pregnant during the trial, the combination treatment must immediately be interrupted. The patient will be followed up until delivery or termination of pregnancy (see [Section 5.3.7](#)). The data of the patient will be collected and reported in the Clinical Trial Report (CTR) until last patient last visit and any events occurring thereafter will be reported in BI drug safety database.

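### Protocol 4.1.4.5: for several rows, the two BI 836826 dose-modification tables give different instructions when a related adverse event recurs

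*Protocol*

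**What the plan says.** Protocol 4.1.4.5 first tabulates actions by the worst finding after the previous dose. Three of its rows delay the infusion until recovery and then direct: "Thereafter resume at full dose". They are neutrophils 0.5 to <1 x10^9/L (or <0.5 for up to 7 days), Grade 2 ALT/AST and Grade 2 bilirubin. None of the three says what to do if the finding comes back.

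The more severe rows do have a recurrence rule. For neutrophils <0.5 x10^9/L for more than 7 days, platelets at or below 10 000/µL on two measurements, and Grade 3-4 ALT/AST or bilirubin, full dose may be resumed after the first event and is halved on recurrence. For neutrophils the halving depends on recurrence despite G-CSF. The hepatic rows also allow a return to 100% later. For other non-haematological events of Grade 3 or more: "Study drug may be resumed at initial or lower dose level or discontinued at investigator's discretion".

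A linking sentence follows: "A dose reduction of BI 836826 may be performed twice as outlined in the next table". The second table is headed "Occurrence of a BI 836826 related AE included in previous table". Its first step is "Restart at assigned dose" and its second is "Reduce BI 836826 by 50% at next infusion (dose level -1". The third is a 75% reduction from the assigned dose, and the fourth is discontinuation.

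Protocol 3.3.4.1 refers to 4.1.4.5 for one optional withdrawal ground: "The patient is not able to tolerate a second re-challenge for the same AE".

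**The concern.** The second table's header has no limit by grade or row, so on its wording it reaches the three rows that return the patient to full dose every time. A site that follows the first table keeps the patient at 100%. A site that follows the second halves the dose, halves it again and then stops. Both can say they followed the protocol.

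The neutrophil row matters most. Protocol 1.2.1 and 2.3 describe neutrophils falling immediately after infusion, and 1.2.1 reports related Grade 3-4 neutropenia in 14 of 36 patients (39%) in trial 1270.1.

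Two things are at stake:

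- **Patients.** Protocol 2.1 lets those on treatment complete the trial under the protocol, potentially to Cycle 24, so dosing and discontinuation still depend on these tables.
- **Reporting.** The SAP tabulates events leading to dose reduction or discontinuation (7.8.1.2) by initial dose cohort (6.1), and judges compliance by whether BI 836826 was given according to protocol (7.3). Violation code C2 (6.2) flags any infusion in Cycles 2-24 not given at 100%. A reduction made in good faith under the second table could be flagged as a violation.

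**Working it through.** **Check of the plan's own figure.** Third step of the second table: two successive halvings leave 0.5 x 0.5 = 0.25 of the assigned dose, a reduction of 1 - 0.25 = 75%. This matches the table.

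**Row by row.** Entries are percentages of the assigned dose. At the first occurrence the second table restarts at 100%. At the second, third and fourth it gives 50%, 25% and stop for every row it covers. Rows are identified by grade label, because the numerical range printed for Grade 3-4 bilirubin is the same as for Grade 2.

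| First-table row | First table on recurrence | Compared with the second table |
|---|---|---|
| Neutrophils 0.5 to <1, or <0.5 for up to 7 days | 100%, 100%, 100% | Conflict at 2nd, 3rd and 4th |
| Grade 2 ALT/AST | 100%, 100%, 100% | Conflict at 2nd, 3rd and 4th |
| Grade 2 bilirubin | 100%, 100%, 100% | Conflict at 2nd, 3rd and 4th |
| Neutrophils <0.5 for more than 7 days | 50% only if it recurs despite G-CSF | Agrees if G-CSF was given; otherwise differs |
| Platelets at or below 10 000/µL, twice | 50% | Agrees; second table adds later steps |
| Grade 3-4 ALT/AST or bilirubin | 50%, later return to 100% allowed | First reduction agrees; second table has no return step |
| Other non-haematological, Grade 3 or more | Investigator's choice | Partial mismatch: choice versus fixed steps |
| Rows that maintain dose and schedule | Unchanged | Conflict only if the header is read with full literalness |

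**Planned exposure over 12 cycles** (infusion schedule in Protocol 4.1.1):

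- Cycle 1: 10 mg, then 0.5 + 0.5 + 1 = 2 times the assigned dose (4 infusions)
- Cycles 2-4: 3 x 2 = 6 times (6 infusions)
- Cycles 5-12: 8 x 1 = 8 times (8 infusions)
- Total: 2 + 6 + 8 = 16 times plus 10 mg, in 4 + 6 + 8 = 18 infusions, the synopsis figure

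**Illustration: one patient with neutrophils 0.5 to <1 x10^9/L.** Assume that counting starts with Cycle 1 Day 15, that each nadir is judged related to BI 836826, and that recovery is quick enough for no infusion to be omitted. Totals exclude the 10 mg pre-dose.

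- First table: every infusion at 100%, so up to 16 times.
- Second table, nadir after every infusion including the reduced ones: 0.5 (C1D2) + 0.5 (C1D8) + 1 (C1D15) + 1 (C2D1, after the first occurrence) + 0.5 (C2D15) + 0.25 (C3D1), then stop. Sum 3.75 times; 3.75/16 = 23%.
- Second table, nadir only after full-dose infusions: two occurrences, then the 13 remaining infusions at 50%. 0.5 + 0.5 + 1 + 1 + 13 x 0.5 = 9.5 times; 9.5/16 = 59%.

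**The case against.** The best defence is that the tables work together: the first says when to reduce, and the second only sets the size of successive reductions. The linking sentence is permissive, the section is titled as recommendations, and the severe rows fit this reading. It is reasonable, and may be what was meant. But nothing limits the second table to it: the header covers every related event in the first table, and the opening step is a restart, not a reduction.

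Other limits stand, and they rule out stronger readings that a reader might infer:

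- **That the tables disagree for every repeated event.** They do not. The platelet row and the first reduction for Grade 3-4 hepatic events match the second table, as does prolonged severe neutropenia that recurs despite G-CSF.
- **That 3.3.4.1 adds a contradictory third limit.** It says a patient may be withdrawn, and failing to tolerate a re-challenge is not the same as any third occurrence. The weakness is that 4.1.4.5, to which it refers, never uses the term re-challenge.
- **That most patients will meet the conflict, or that 23% is an expected exposure.** The 39% is worst grade over doses of 1 to 800 mg, with no recurrence data. Counts recovered by Day 8 in most patients, and from Cycle 2 the Flow Chart schedules blood counts on dosing days and at response visits, so many short nadirs would go unrecorded.
- **That dose escalation is compromised.** Escalation uses Cycle 1 DLTs, and uncomplicated Grade 3-4 neutropenia is not a DLT (5.3.6.2). Recruitment is stopped and an abbreviated report is planned (SAP 3).

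The SAP's listing of all BI 836826 administrations (7.3) will show the doses given, but not which rule produced a change.

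**Conclusion.** The point holds for specific rows. Three rows of the first table conflict directly with the second from the second occurrence onward: 100% against 50%, then 25%, then discontinuation. Three lesser mismatches concern prolonged severe neutropenia, re-escalation after Grade 3-4 hepatic events, and other non-haematological events of Grade 3 or more.

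For a patient with repeated qualifying nadirs, exposure over 12 cycles could be 16 times the assigned dose under one table and 9.5 times (59%) or 3.75 times (23%) under the other. These figures rest on the relatedness, recovery and recurrence assumptions in the working. They are not averages, and the documents do not allow a frequency to be attached.

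The effect on Cycle 1 DLT counts and the RP2D is small. Reconciliation is still needed, because the instructions govern dosing and discontinuation for patients still on treatment. Which rule is right is a clinical decision and is not judged here.

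**What to change.** Reconcile the two tables in Protocol 4.1.4.5 by stating:

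- which rows of the first table count as an occurrence for the second;
- whether occurrences are counted per adverse event or across events;
- which table governs where they differ, including the G-CSF condition, re-escalation after hepatic events and investigator's discretion.

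Align the cross-reference and the re-challenge wording in 3.3.4.1 with the result. The sponsor's clinical team decides the rule.

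Send the clarification to sites with patients still on treatment. For patients already treated, flag in the dose-reduction, discontinuation and protocol-violation (SAP 6.2, code C2) listings which rule was applied, so that a reduction made under the second table is not read simply as a violation.

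The cost is a protocol clarification, a site letter and a reporting flag for some past dose changes. No extra patient procedures are needed.
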